9.3. Subsequent Visits

Part 1: logging events

At each consultation, either through phone or face to face visit, the clinician who contacts the patient will log on the spreadsheet the distance walked and a series of study-related events, marked with a code. Coding is needed to simplify and automate later analysis. The following is an example of the structure of the spreadsheet:

Patient number	hospital	Date	Event	Comments

Events codes are explained in the following table:

Event	Code	Example comments
The patient accepts to join the study and provides consent.	RECRUIT-ACCEPT	Patient has accepted to join the study.
The patient denies consent and does not join the study.	RECRUIT-DENY	Patient denies consent because of lack of time.
The patient has decided to withdraw from the study.	RECRUIT-WITHDRAW	Patient's conditions have worsened and she cannot walk 6 minutes any more.
The patient declares to have the app installed on a phone he/she can use.	APP-OK	Patient has downloaded the app, everything works as expected.
The patient declares that he/she is having technical issues with the app.	APP-ISSUE	The app crashes when started on iPhone 11.
The patient shares a 6MWT not older than 2 weeks either through email or by telephone.	APP-6MWT	Date: 3/5/2021, distance: 420 m
The patient needs further evaluation because of changed medical conditions. The role of the app-based 6MWT is also coded depending on whether it was irrelevant to the decision, partially involved or fundamental for the decision. The event is logged once per decision (further contacts with the patient resulting from the decision should not include the tag).	NEW-EVAL-NO-6MWT NEW-EVAL-PART-6MWT NEW-EVAL-FULL-6MWT	The patient shows a general deterioration, last 6MWT was below 300m. An MDT is required.
The patient needs a change in the treatment. The role of the app-based 6MWT is specified as above.	NEW-TREAT-NO-6MWT NEW-TREAT-PART-6MWT NEW-TREAT-FULL-6MWT	Medication regime increased because of a lower 6MWD in the last 4 weeks.

Regular clinic 6MWT	CLINIC-6MWT	Date: 23/4/2021, distance: 450m
Additional observations	EXTRA-OBS	Because of reduced risk of corona infection, patient is invited to the clinic.

A list of possible codes with their explanation will be included in a tab of the spreadsheet.

Part 2: accuracy, usability and acceptance assessment

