9.5. Early Discontinuation/Withdrawal of Participants

During the course of the trial a participant may choose to withdraw early from the trial treatment at any time. This may happen for a number of reasons, including but not limited to:

- The occurrence of what the participant perceives as an intolerable AE.
- Inability to comply with trial procedures
- Participant decision

Participants may choose to stop study assessments but may remain on study follow-up.

Participants may also withdraw their consent, meaning that they wish to withdraw from the study completely. Patients are allowed to withdraw at any time. In case of withdrawal, they will communicate it to the staff who will log the withdrawal on the spreadsheet together with the reason. The patients will remain under regular active follow up

- 1) Participants can withdraw from the study but permit data obtained up until the point of withdrawal to be retained for use in the study analysis. No further data would be collected after withdrawal.
- 2) Participants can withdraw completely from the study and withdraw the data collected up until the point of withdrawal. The data already collected would not be used in the final study analysis.

In addition, the Investigator may discontinue a participant from the trial treatment at any time if the Investigator considers it necessary for any reason including, but not limited to:

- Pregnancy

The type of withdrawal and reason for withdrawal will be recorded in the CRF.

If the participant is withdrawn due to an adverse event, the Investigator will arrange for follow-up visits or telephone calls until the adverse event has resolved or stabilised.

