10. TRIAL INTERVENTIONS

Not applicable

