We will estimate the time spent in hospital attendances and the number of hospital visits made during the study period and compare it with previous 5 years.

Compare the use of 6MWT during pandemic with standard care.

We will compute statistics regarding the number of 6MWT available per patient over the last 5 years and compare them with the number of available 6MWT results within the study period. This will help identify the difference between the number of 6MWT per patient per year before the pandemic (standard 6MWT in clinic) and after the pandemic (using the app).

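### The Part 1 log's single withdrawal code, illustrated by a patient who can no longer walk, risks merging inability to test with withdrawal and losing data after deterioration

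*Combined protocol and SAP*

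**What the plan says.** The event table under Subsequent Visits (Part 1) has one code for leaving the study, RECRUIT-WITHDRAW, defined as "The patient has decided to withdraw from the study". The example comment beside it reads "Patient's conditions have worsened and she cannot walk 6 minutes any more".

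Section 9.5 describes three situations:

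- Stopping tests only: "Participants may choose to stop study assessments but may remain on study follow-up".
- Withdrawing with earlier data kept: "No further data would be collected after withdrawal".
- Withdrawing with earlier data removed: "The data already collected would not be used in the final study analysis".

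Section 9.5 lists inability to comply with trial procedures among the reasons for leaving early. It has staff log the withdrawal and its reason on the spreadsheet, and adds: "The type of withdrawal and reason for withdrawal will be recorded in the CRF". It refers to withdrawal from trial treatment, whereas section 10, on trial interventions, reads "Not applicable".

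Section 12.1 bases the Part 1 analysis on the spreadsheet labels, so that no manual coding is needed. The management outcome comes from the evaluation codes. For hospital use the plan is: "We will estimate the time spent in hospital attendances and the number of hospital visits made during the study period", compared with the previous 5 years. Section 12.3 defines the analysis population as all participants and gives no rule for those who withdraw.

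**The concern.** The example describes loss of ability, not withdrawal of consent. A clinician who uses the table as a guide could log such a patient as withdrawn, and under section 9.5 collection then stops. Most Part 1 outcomes still wanted from her need no app test: further evaluations, treatment changes, clinic walk tests and hospital visits all arise in routine care.

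The loss would be tied to prognosis. Section 5.4 says that detected deterioration leads to an invitation to clinic, so the time after deterioration is likely to hold more visits and decisions than stable time. Removing it from the study period, but not from the previous 5 years, would make visits in the app period look fewer. Later management decisions would also go uncounted. For the primary objective, which asks whether patients are able and willing, one label would cover both those no longer able and those no longer willing.

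**Working it through.** **Step 1: set the passages side by side.**

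| Situation in section 9.5 | Code in the Part 1 log | Recorded elsewhere |
|---|---|---|
| Stops tests, stays in follow-up | none | no provision stated |
| Withdraws, earlier data kept | RECRUIT-WITHDRAW | type and reason in CRF; reason on spreadsheet |
| Withdraws, earlier data removed | RECRUIT-WITHDRAW | type and reason in CRF; reason on spreadsheet |

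The log cannot show the first situation and does not separate the other two. The example attached to the only available code fits the first situation at least as well as the others. Two further passages point the same way: inability to comply is listed in 9.5 as a reason for early withdrawal, and inability to complete the walk is an exclusion criterion in 8.3.

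**Step 2: see what would be lost.** The management outcome is built from log codes, so decisions after a logged withdrawal are missing from it. The log has no code for hospital visits or time in hospital, and section 12.1 names no source for them. That outcome is affected only where the rule against further data is applied to the patient.

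**Step 3: illustrate the size.** The plan gives no withdrawal rate or visit rate, so it has no figure to reproduce. The inputs below are assumptions.

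- d = share of participants who deteriorate and are logged as withdrawn at month 6 of 12.
- r = visit rate after deterioration, relative to a stable rate of 1.

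True mean = (1 − d) + d(0.5 + 0.5r).
Recorded mean per person-year, censored at withdrawal = 1.
Recorded mean per enrolled patient, with unobserved time counted as zero visits = (1 − d) + 0.5d.

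For d = 10%:

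- r = 2: true 1.05. Per person-year 1/1.05, 4.8% low. Per patient 0.95/1.05, 9.5% low.
- r = 3: true 1.10. 9.1% and 13.6% low.
- r = 4: true 1.15. 13.0% and 17.4% low.

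Understatement, per person-year / per enrolled patient:

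| d | r = 1 | r = 2 | r = 3 | r = 4 |
|---|---|---|---|---|
| 2% | 0 / 1.0% | 1.0 / 2.0% | 2.0 / 2.9% | 2.9 / 3.9% |
| 5% | 0 / 2.5% | 2.4 / 4.9% | 4.8 / 7.1% | 7.0 / 9.3% |
| 10% | 0 / 5.0% | 4.8 / 9.5% | 9.1 / 13.6% | 13.0 / 17.4% |
| 20% | 0 / 10.0% | 9.1 / 18.2% | 16.7 / 25.0% | 23.1 / 30.8% |

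The d = 10%, r = 4 cell in counts, for an assumed 300 participants with 1 visit per 6 months when stable and 4 per 6 months afterwards:

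- True visits: 270×2 + 30×(1 + 4) = 690, or 2.30 per patient.
- Recorded visits: 270×2 + 30×1 = 570.
- Per enrolled patient: 570/300 = 1.90, 17.4% low.
- Per person-year: 570/(270 + 15) = 2.00, 13.0% low.

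At the planned 250–500 participants, d = 10% means 25–50 people.

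**The case against.** A reader might infer that deteriorating patients must be withdrawn and so leave data collection altogether. The documents do not say that. The code is defined by the patient's own decision, the sentence about walking is only an example comment, and section 9.5 keeps the option to stop tests and stay. This stands, so the point is a risk of miscoding, not a rule.

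Deterioration also has its own codes. NEW-EVAL covers changed medical conditions, has a variant in which the app test played no part, and can be logged before any withdrawal. It is logged once per decision, so follow-on contacts are not counted anyway. This stands too: only later, separate decisions are at risk.

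The reason for withdrawal goes on the spreadsheet, and type and reason go in the CRF, so a patient too ill to test could be told apart from an unwilling one. That is correct, but it takes a step outside the label-driven analysis of section 12.1, and it cannot recover data that were never collected.

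A reader might also infer that the hospital-visit comparison is biased, or take 17% as the size of the bias. Neither is established. The source of visit data is not stated. The 17% needs a fourfold visit rate and counts unobserved time as zero visits; the same inputs give 13% per person-year. Both outcomes are secondary and descriptive.

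**Conclusion.** The concern holds as a mismatch between the event table and section 9.5 that could cause data loss linked to deterioration. It could lower the count of later management decisions. It could also lower study-period hospital visits where further collection is stopped, and for visits the direction favours the app whenever the visit rate rises after deterioration.

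The true size cannot be computed from the documents. With 10% deteriorating at mid-study, all logged as withdrawn, and a visit rate 2–4 times higher afterwards, the understatement is about 5–13% per person-year or 10–17% per enrolled patient. If the visit rate does not rise, the person-year bias is zero, and the per-patient figure is still 5% low because unobserved time counts as zero. The change is cheap and worth making before data collection, since the loss cannot be repaired afterwards.

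**What to change.** 1. In the Part 1 event table, add a dated code for participants who stop app tests but remain in follow-up, with a reason (for example cannot walk, phone or app problem, prefers clinic test, other). Move the example about being unable to walk to that code.
2. Reserve RECRUIT-WITHDRAW for withdrawal of consent, and split it by the two data options in section 9.5.
3. In section 9.5, state that routine consultation, hospital-visit and clinic 6MWT data continue to be collected unless consent is withdrawn. Reconcile its references to trial treatment with section 10.
4. In section 12.1, report visit and management outcomes as rates per person-time, with withdrawals counted by reason.

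The cost is one or two extra codes and wording changes in sections 9.5 and 12.1 and the information sheet. No extra visits are needed. Rates per person-time do not by themselves remove the bias when the visit rate rises after deterioration; continued collection under items 1 to 3 is what prevents it.

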12. STATISTICS

12.1. Description of Statistical Methods

The analysis of the data involves reviewing the spreadsheet. The use of the labels will simplify analysis and will avoid manual coding. The R programming environment will be used to compute statistics.

To assess whether patients are able and willing to use a smartphone app for the 6MWT.

For each recruited patient, we will compute the number of app-based 6MWT results available since they confirmed that they have downloaded the app. From this number, we will compute a histogram of the number of available app-based 6MWT per patient and the percentage of participants who perform at least one app-based 6MWT prior to every consultation.

To assess the accuracy of the app-based measurement.

We will compare the walked distance measured by the app with the distance measured by the trundle wheel for those tests that provide both information. We will compute descriptive statistics (mean, standard deviation, percentiles) of the difference and BlandAltman plots.

To assess whether differences in distance walked according to the app altered management of patients.

We will use the codes related to clinical evaluations to compute descriptive statistics about the frequency of those evaluations and about how many of them were triggered by observed changes of the 6MWD.

To assess the usability and acceptance of the app.

We will compute descriptive statistics of the results of the usability and acceptance questionnaires. We will use thematic content analysis to analyse the interview transcripts.

To collect raw data from phones' sensors to allow the development of future algorithms for app-guided 6MWT.

We will also use the sensors data sent from patients involved in part 2 of the study to identify strategies to improve the algorithm that computes the distance. The availability of this type of data would be unique and would open interesting research in computer science and biomedical engineering. The University of Malmo is planning to experiment signal processing (Kalman filters, FIR filters) and machine learning (LSTM RNN) techniques to improve the accuracy of the current GPS-based algorithm and to explore the possibility to develop an indoor version of the algorithm based purely on the inertial sensors (acceleration).

To determine whether the use of the 6MWT reduces time spent and number in hospital visits.

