13. DATA MANAGEMENT

13.1. Data Recording and Record Keeping

Part1

The data will be collected using an electronic spreadsheet shared by the team at OUH. Patients will be asked about their recent app-based 6MWTs during visits or phone calls and will be invited to share the log of their app-based 6MWTs by email or telephone with the clinician. If patients have technical problems and need assistance, they can contact the team in Sweden, who are responsible for the development of the Timed Walk app. In this case, the patient can disclose their identity to the team in Sweden if they wish.

Every 3 months, the spreadsheet will be anonymised by substituting the patient hospital number with an internal ID and sent to Malmo University for analysis in an encrypted email.

Part 2

Results of the additional 6MWTs performed by the subgroup of 15 patients will be shared by email with the team in Malmo. We will seek explicit consent to share these data, both as identifiable information for the researchers in Sweden and in an anonymous format publicly.

In order to anonymise the data before publication, the following strategy will be used:

- Email addresses will be removed and an internal patient ID will be used to group tests belonging to the same user.
- Timestamps will be formatted only in relation to the start of the test.
- Location data will be anonymised using a random offset on both longitude and latitude (resulting in the trace to keep its original shape, but the position to be placed in a random place).
- Any unique identifier of the phone will be removed, but the make and model may be kept in order to compare different phones characteristics.

Electronic questionnaires for usability and acceptance will be set up using Microsoft Forms. Malmo University has an agreement with Microsoft to use the product for research purposes and guarantees

that data is protected according to the GDPR. The questionnaire will not require personal information to be collected and will be deleted after analysis.

Audio recording of the interviews will be collected by OUH and sent electronically to Malmo University for analysis. These files will not be linked to the identity of the patient, they will be transcribed and deleted immediately after. All files containing patients' anonymised data exchanged between Malmo and OUH will be encrypted using a password which will be communicated verbally during a phone call.

Paper forms will be kept by the Principal Investigator at OUH.

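### App walks enter the log only if at most 2 weeks old, yet that log feeds a count since download and a yearly comparison with clinic tests that have no age limit

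*Combined protocol and SAP*

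**What the plan says.** Section 9.3 (Subsequent Visits) sets up the Part 1 log. Entries are made at contacts: "At each consultation, either through phone or face to face visit, the clinician who contacts the patient will log on the spreadsheet the distance walked", together with coded events. APP-6MWT is the only code for an app test. Its definition is: "The patient shares a 6MWT not older than 2 weeks either through email or by telephone". The text does not say whether the age of the test is counted back from the consultation or from the moment of sharing. The code for clinic tests in the study period, CLINIC-6MWT, is described only as "Regular clinic 6MWT" and has no age limit.

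Section 12.1 names this log as the data source: "The analysis of the data involves reviewing the spreadsheet". The labels are meant to make manual coding unnecessary. Two outputs matter here:

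- For app use, the plan states for each patient: "we will compute the number of app-based 6MWT results available since they confirmed that they have downloaded the app". A histogram of tests per patient follows.
- For use before and during the pandemic, it takes the 6MWTs per patient over the last 5 years and will "compare them with the number of available 6MWT results within the study period", expressed per patient per year.

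The historical tests come from the electronic health record by patient ID and date, with no age limit (Section 9.2, Baseline Assessments). Under Section 13.1 (Part 1), patients are also "invited to share the log of their app-based 6MWTs by email or telephone with the clinician".

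**The concern.** A 2-week window suits the question of whether a recent walk was available for a consultation. It does not suit a count since download or a yearly rate, which accumulate over the whole period. A walk done between contacts and older than 2 weeks has no code. If a clinician notes it as a free-text comment, an analysis that relies on labels will not count it. The 3-monthly quality check in Section 14 looks at keywords, spelling and consistency, so it would not obviously show the gap.

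At stake is the meaning of two descriptive outputs. In the yearly comparison, the app side passes through an age filter and the clinic side does not, so part of any difference would come from the logging rule and not from patient behaviour. Tests that were never logged may not be recoverable at the end of the study.

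**Working it through.** The plan states no expected test rate, consultation interval or capture rate, so there is no figure to reproduce. The window of 14 days is from Section 9.3. Every interval and test rate below is an assumption, shown over a range.

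**1. Capture.** If age is measured at the consultation and every walk inside the window is logged, the captured share equals the share of walks done in the 14 days before a contact. With walks spread evenly and contacts every I days, capture = min(1, 14/I).

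| I (days) | Capture | Logged per year if 12 are done | Logged per year if 52 are done |
|---|---|---|---|
| 14 | 100% | 12 | 52 |
| 28 | 14/28 = 50% | 6.0 | 26.0 |
| 56 | 14/56 = 25% | 3.0 | 13.0 |
| 91 | 14/91 = 15.4% | 1.85 | 8.0 |
| 182 | 14/182 = 7.7% | 0.92 | 4.0 |
| 365 | 14/365 = 3.8% | 0.46 | 1.99 |

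If walks are done only in the 2 weeks before each contact, capture is 100% at any interval. The same holds if each walk is shared promptly and age is measured at sharing, provided it is then logged.

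**2. Yearly comparison.** Assume one clinic test per consultation before the pandemic, so 365/I clinic tests a year, and T evenly spread app tests a year in the study.

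- True ratio, app to clinic = T × I/365.
- Logged ratio = T × (14/I) ÷ (365/I) = 14T/365.
- I = 91 (about 4 clinic tests a year), T = 12: true 2.99, logged 0.46. The direction reverses.
- I = 91, T = 52: true 12.96, logged 1.99. The direction holds, but the ratio shrinks.

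Under these assumptions reversal needs T above 365/I and below 365/14, which at 91 days is between about 4 and 26 tests a year.

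**3. Histogram.** At 91 days, the patient who walks 12 times a year shows 1.85 tests and the one who walks 52 times shows 8.0 (about 2 per consultation). The log still separates them, but on a compressed scale.

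**4. Primary percentage.** With Poisson walks at 12 a year, the chance of at least one in 14 days is 1 − exp(−12 × 14/365) = 36.9%. Over 91 days it is 1 − exp(−12 × 91/365) = 95.0%. The window is therefore part of the meaning of a test before consultation. Keeping it there leaves that outcome as it is, but its reference date has to be stated.

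**The case against.** The case on the other side has several parts.

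- **Available may mean logged.** Section 12.1 counts available results, so a reader who infers that the plan promises to count every walk goes further than the text. This stands. It does not cure the comparison, where the same word is used for both sides and only the app side has an age limit.
- **The reference date is open, and patients can share by email or telephone.** If age is measured at sharing, prompt sharers lose nothing. This stands, and is why zero loss is within the range.
- **Section 13.1 invites patients to share their log.** It does, but no code or rule brings older entries into the analysed data.
- **The window may be deliberate, and walks may cluster before contacts.** Both are plausible, since the primary outcome concerns a test before consultation. That supports the window for the primary outcome, not for a yearly rate.

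Stronger readings are tempting, and the documents do not support them. Severe undercounting is not established without an interval or test timing. Nor is it established that the health record holds every past clinic test: Section 9.2 says only that the data are pulled from it. The example comment "Medication regime increased because of a lower 6MWD in the last 4 weeks" might be taken as proof that the log cannot support such a decision, but two contacts about 2 weeks apart, each with a recent walk, would put that trend in the log. A histogram stuck at 0 or 1 per consultation whatever the true use is contradicted by step 3, and reversal of the comparison is conditional, as step 2 shows.

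**Conclusion.** Wrong as written. One age-limited code supplies a cumulative count and a yearly rate, and the rate is compared with clinic tests that have no such limit. The rule can only lower the app count, and nothing in the log shows by how much. The loss runs from 0% (contacts at most every 2 weeks, walks timed to consultations, or prompt sharing with age measured at sharing) to 84.6% at 91-day and 96.2% at 365-day intervals with evenly spread walks and age measured at the consultation. The direction of the yearly comparison could reverse under some of these assumptions and not under others.

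The effect is confined to the histogram and the descriptive secondary comparison of use. A reader might infer that the primary percentage fails too. It does not, provided the window is kept there and its reference date is stated.

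**What to change.** 1. In Section 9.3, redefine APP-6MWT so that one row, with the test date, is entered for every app test the patient shares since the previous contact. Alternatively, import the shared log that Section 13.1 already invites.
2. State the date from which the 2 weeks are counted, and apply that window only when deriving the primary outcome.
3. In Section 12.1, use all dated rows for the histogram and the per-year comparison, divided by each patient's own follow-up time. Count clinic tests by the same rule.
4. Where logs are not shared in full, describe the app count as a lower bound.

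The cost is a changed code definition and more data entry, which grows with use: about 12 rows a year for a monthly walker and 52 for a weekly one. At the planned 250 to 500 patients, weekly walking by everyone would mean 52 × 250 = 13,000 to 52 × 500 = 26,000 rows a year, so importing logs would be preferable for frequent walkers. If the sponsor keeps the present code, the minimum is to label both outputs as counts of recent shared tests and to make no claim about yearly use against clinic tests.
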